9.1 General Considerations

All statistical tests will be performed using a two-sided test at a 5% significance level.

If the trial is stopped prematurely due to e.g. futility, the data will be analysed as planned in this statistical analysis plan.

All efficacy endpoints will be analysed for the FAS analysis set, and as a sensitivity the analyses for the primary endpoint will be repeated for the PP population.

Categorical data will be summarised using counts and percentages, while continuous data will be presented using the number of patients (N), mean, standard deviation, median, interquartile range, minimum and maximum. All efficacy endpoints will be listed in patient data listings.

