7	Nov 9 - 2017	Additional analyses to MAP analyses. Analysis for duration of septic shock changed from ANCOVA to negative binomial (as blinded data suggests a better fit) with permutation test as backup in case model assumptions do not hold. Analyses for duration of ventilation and duration of RRT changed from ANCOVA to zero inflated negative binomial (as blinded data suggests a better fit) also with permutation test as backup in case model assumptions do not hold. Analysis for ICU length of stay and hospital length of stay changed from ANCOVA to permutation test (as blinded data suggested a non-parametric model). Covariates were dichotomized accordingly. Appendix 4 removed as no longer needed. Appendix 3 updated with variance correction for difference in PVFDs Analyses in 9.4.8, 9.4.9, and 9.4.10 will not be repeated for the selected arm only and data from part 2 only, as they are measured on a subset of patients, probably only in part 1. A "time" by "baseline value" interaction term has been added to the repeated ANCOVA analyses in 9.3.1.5, 9.3.3.1, 9.3.4.1, 9.3.4.2, and 9.4.5 as it is likely that the trajectory over time for each patient will depend on the baseline value. The supportive competing risk and Kaplan-Meier graphs for duration of RRT has been taken out as it makes no sense since RRT durations are short and repetitive. It is more meaningful to just look at 90 day mortality. For the remaining 'duration' endpoints withdrawal rates has been added to the competing risk and Kaplan-Meier graphs. As this is a superiority trial, the PP analysis will only be performed for the primary endpoint, and hence not performed for secondary as previously stated.	Version 6

Date: 20 Nov 2017 E-Statistical Analysis Plan-17877; Ver.9.0 Supersedes: Ver. 8.0 Page 5 of 80

		Only major protocol deviations will be listed. Adverse events graphs added to output. Fluid balance analyses updated. Analyses for norepinephrine/noradrenaline and other vasopressor doses updated. Forest plots added for incidence of RRT (section 9.3.1.8) and mortality (section 9.3.2.3).	
8	Nov 9 - 2017	Format change only. No content was changed	Version 7
9	Nov 20 - 2017	Format change only. No content was changed	Version 8

Page 6 of 80

Signed agreement on Statistical Analysis Plan

TABLE OF CONTENTS

1	Intro	ductionduction	10			
	1.1	Definitions/ Abbreviations	10			
		1.1.1 Definition of Terms	10			
		1.1.2 Abbreviations	10			
2	Trial	Objectives and Endpoints	12			
	2.1	Objectives	12			

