Incidence of RRT will be analysed by a logistic regression model with time from onset of shock to start of treatment, baseline creatinine and norepinephrine/noradrenaline requirement at baseline (µg/kg/min) as covariates, and treatment and need for ventilation as factors. The 95% confidence interval for the difference in proportions between treatment groups will be constructed using the delta method (see Appendix 4 for details). Patients already on RRT for chronic renal failure at time of inclusion will be excluded from the analysis of incidence of RRT.

Non-inferiority will be claimed if the upper limit of the two-sided 95% CI of the adjusted difference in proportions is less than 20% of the estimated incidence of RRT in the placebo group. Superiority can be claimed (5) if the upper limit is less than 0.

I.e., let $\widehat{p_S}$ and $\widehat{p_P}$ be the estimated incidences of RRT in the combined selepressin groups and the placebo group respectively. Non-inferiority will then be claimed if

$$\widehat{p_S} - \widehat{p_P} + 1.96 * \sqrt{var(\widehat{p_S} - \widehat{p_P})} < 0.2 * \widehat{p_P}$$

and superiority will be claimed if

$$\widehat{p_S} - \widehat{p_P} + 1.96 * \sqrt{var(\widehat{p_S} - \widehat{p_P})} < 0$$

A forest plot including the non-inferiority tests for all analyses will be presented.

Furthermore, incidence of RRT will be tabulated by treatment arm (including pooled active treatment arms).

A subgroup analysis will be performed on patients without acute RRT at baseline.

9.3.1.9 Duration of RRT up to Day 90 (excluding patients on RRT for chronic renal failure at time of randomisation)

Duration of RRT is defined as the cumulative periods with RRT (continuous renal replacement therapy, intermittent hemodialysis or peritoneal dialysis) and will be analyzed excluding patients on RRT for chronic renal failure at time of randomisation.

For patients withdrawn or dying while still on RRT, the duration will be based on the data available up until the time of withdrawal or death.

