9.3.2 Morbidity/Mortality

9.3.2.1 Intensive Care Unit (ICU)-free Days up to Day 30

ICU -free Days up to Day 30 will be defined and analyzed in a similar manner as the primary endpoint, with the van Elteren test stratified by need for ventilation (Yes/No), time from onset of shock to start of treatment (< or \ge 6 hours), and norepinephrine/noradrenaline requirement at baseline (< or \ge 30 µg/min) and baseline creatinine (< or \ge 150 µmol/L).

A sensitivity analysis will be performed where the definition of time spent in the ICU will include first admission to emergency department, as some patients will be enrolled and have first IMP treatment in the emergency department.

9.3.2.2 ICU Length of Stay up to Day 30

ICU length of stay is defined as the cumulative periods spent in ICU from start of IMP to 30 days after.

For patients withdrawn or dying while still in ICU up to Day 30, the duration will be based on the data available up until the time of withdrawal or death.

ICU length of stay will be analyzed between treatment groups using the permutation test specified in Section 9.3.1.3 stratified by the combination of time from onset of shock to start of treatment (< or \ge 6 hours), baseline creatinine (< or \ge 150 μ mol/L), norepinephrine/noradrenaline requirement at baseline (< or \ge 30 μ g/min) and need for ventilation (Yes/No).

A sensitivity analysis will be performed where the definition of time spent in the ICU will include first admission to emergency department, as some patients will be enrolled and have first IMP treatment in the emergency department.

9.3.2.3 All-cause Mortality (Defined as the Fraction of Patients That Have Died, Regardless of Cause, by the end of Day 30, Day 90, and Day 180)

Mortality will be analysed by a logistic regression model with the individual SOFA scores and age as covariates and treatment arm as factor. The 95% confidence interval for the difference in proportions between treatment groups will be constructed using the delta method as for incidence of RRT (section 9.3.1.8). There will be no imputations for mortality.

Non-inferiority will be claimed if the upper limit of the two-sided 95% CI of the adjusted difference in proportions is less than 30% of the estimated incidence of mortality in the placebo group. Superiority can be claimed (5) if the upper limit is less than 0.

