I.e., let $\widehat{p_S}$ and $\widehat{p_P}$ be the estimated incidences of mortality in the combined selepressin groups and the placebo group respectively. Non-inferiority will then be claimed if

Page 36 of 80

$$\widehat{p_S} - \widehat{p_P} + 1.96 * \sqrt{var(\widehat{p_S} - \widehat{p_P})} < 0.3 * \widehat{p_P}$$

and superiority will be claimed if

$$\widehat{p_S} - \widehat{p_P} + 1.96 * \sqrt{var(\widehat{p_S} - \widehat{p_P})} < 0$$

Assuming observed mortality rates of 20-25% in the placebo group, a non-inferiority limit of 30% corresponds to a maximum observed mortality rate of 2-3% in the combined selepressin groups in order for selepressin to be non-inferior to placebo. A forest plot including the non-inferiority tests for all analyses will be presented.

Furthermore, mortality will be tabulated by treatment arm (including pooled active treatment arms), and the time to death presented graphically by a Kaplan-Meier plot.

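### The mortality and RRT non-inferiority claims rest on the full analysis set alone, because the per-protocol repeat is confined to the superiority primary endpoint

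*SAP*

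**What the plan says.** Section 9.1 puts all efficacy endpoints on the FAS and then adds that "as a sensitivity the analyses for the primary endpoint will be repeated for the PP population". The change log entry for version 7 explains the restriction: "As this is a superiority trial, the PP analysis will only be performed for the primary endpoint, and hence not performed for secondary". Section 9.1 is the rule in force, and the log shows the reasoning behind it.

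Two secondary endpoints carry non-inferiority rules. For RRT incidence (9.3.1.8), the claim is made if the upper limit of the 95% CI for the adjusted difference "is less than 20% of the estimated incidence of RRT in the placebo group". For all-cause mortality (9.3.2.3), it is made if that limit "is less than 30% of the estimated incidence of mortality in the placebo group". In both, superiority may be claimed if the limit is below zero.

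The FAS (6.2) is everyone randomised and dosed. The PP set (6.3) removes FAS patients with major violations as listed in section 5, but uses data up to the point of violation. Section 9.3 repeats the secondary analyses for the selected arm and for Part 2 only, and 9.3.1.8 adds a subgroup without acute RRT at baseline. The Addendum (2.1) defines a stricter PP subset, for the primary endpoint only. No PP check is attached to either non-inferiority claim.

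**The concern.** The stated reason for dropping PP fits a superiority test, where patients without a treatment contrast pull the estimate towards zero and make success harder. In a non-inferiority test the same pull works in favour of the claim: if selepressin does raise mortality or RRT use, such patients shrink the observed excess and help the upper limit stay below the margin. So the reason in the change log does not cover 9.3.1.8 and 9.3.2.3.

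Dilution is plausible on the SAP's own terms. Section 5 lists dosing errors large enough to affect efficacy among the PP exclusions, and those patients stay in the FAS. The Addendum (2.1) also expects some patients to have received norepinephrine in place of IMP for part of the treatment period. At stake are the SAP's only formal statements that selepressin is not worse than placebo on death and RRT. Section 9.1 says data are analysed as planned after a futility stop, so the rules still apply.

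**Working it through.** **Inputs from the SAP.** Margin 30% of the estimated placebo mortality (9.3.2.3); placebo mortality 20-25% ("Assuming observed mortality rates of 20-25% in the placebo group"); upper limit of a two-sided 95% CI; 1800 evaluable patients (3.2); one third on placebo in Part 1, 1:1 in Part 2 (3.1).

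**Assumptions.** A Part 1 of 600 patients gives 600/3 + 1200/2 = 800 placebo and 1000 selepressin. The true excess among non-violators equals the margin. A share v of violators has no treatment difference. The binomial variance is unadjusted, with a normal approximation.

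**The plan's own figure.** Section 9.3.2.3 gives 2-3% as the largest observed selepressin mortality rate compatible with the claim. Solve x + 1.96·√[pP(1−pP)/800 + (pP+x)(1−pP−x)/1000] = 0.3·pP.
- pP = 20%: x = 2.2 points (2.2 + 1.96 × 1.93 ≈ 6.0).
- pP = 25%: x = 3.4 points (3.4 + 1.96 × 2.09 ≈ 7.5).

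The figure therefore reproduces as an excess over placebo. It does not reproduce as a mortality rate, which would be about 22% to 28%. That wording should be corrected, but it is a separate matter.

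**Dilution with a fixed margin, placebo 20%.** Margin = 0.3 × 20 = 6.0 points. SE = √(0.26×0.74/1000 + 0.20×0.80/800) = 1.98 points, held constant. FAS excess = (1−v) × 6.0, so P(claim) = Φ(−1.96 + 6.0v/1.98).
- v = 0: Φ(−1.96) = 2.5%
- v = 10%: Φ(−1.96 + 0.6/1.98) = 4.9%
- v = 20%: Φ(−1.96 + 1.2/1.98) = 8.8%

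**Dilution with the SAP's margin.** The rule compares pS − 1.3·pP + 1.96·SE with zero. The relevant standard deviation is SD = √[1.3²·pP(1−pP)/800 + pS(1−pS)/1000], and P(claim) = Φ((6.0v − 1.96·SE)/SD), all in points.
- v = 0: Φ(−1.96×1.981/2.303) = Φ(−1.686) = 4.6%
- v = 10%: Φ((0.6 − 1.96×1.974)/2.297) = Φ(−1.423) = 7.7%
- v = 20%: Φ((1.2 − 1.96×1.966)/2.290) = Φ(−1.159) = 12.3%

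Dilution thus multiplies the rate by about 1.7 and 2.7. A Monte Carlo check of the same formula at 25% placebo mortality with 767 v 1033 patients gave 4.6%, 8.4% and 14.1%, against 4.7%, 8.5% and 14.2% from the formula.

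**Range (SAP margin, 1000 v 800 unless stated).**

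| Setting | v = 0 | v = 10% | v = 20% |
|---|---|---|---|
| Mortality, placebo 20%, no contrast | 4.6% | 7.7% | 12.3% |
| Same, violators keep half the excess | 4.6% | 6.0% | 7.7% |
| Same, violators carry 1.5 times the excess | 4.6% | 3.5% | 2.6% |
| Mortality, placebo 25%, no contrast | 4.6% | 8.4% | 14.2% |
| RRT, placebo 35% (assumed), no contrast | 3.9% | 6.8% | 11.3% |
| Mortality 20%, no contrast, 533 v 267 (800 in Part 1 only) | 5.1% | 7.0% | 9.5% |

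**Power of a PP analysis at true equality with 10% excluded (SAP margin).** Mortality 25%: 92.5% to 90.0%. Mortality 20%: 84.7% to 81.2%. RRT 35% (assumed): 84.5% to 80.9%. The loss is about 3 points (2.5 to 3.6).

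**The case against.** The best defence is that the direction of the bias is not established. The FAS already leaves out undosed patients, the clearest group with no contrast. Of the eight listed PP exclusions, only dosing errors concern delivery of IMP. The others concern eligibility or status before or at the start of IMP, and such patients may have received IMP as assigned. Nothing in the SAP shows that they lack a treatment effect on death or RRT. Dosing errors need not be under-dosing, so removing them could even hide harm. PP is not protected by randomisation, and section 5 leaves room for judgement-based exclusions. The non-inferiority rules play no part in the Hochberg label procedure, and safety is also covered by section 10 and the mortality futility rule in section 11. The trial stopped for futility, so calculations at 1800 patients are not at its final size.

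All of this stands, and it rules out some stronger readings. A reader might infer that FAS analysis necessarily makes the claim too easy, or that poorer conduct always helps it. The documents support only that it can. A reader might also take a rise from 2.5% to 4.9% as the effect under the SAP's rule. That needs a fixed margin: with the margin estimated from the placebo arm, the rate is already about 4.6% with no violators, which is a separate issue that a PP repeat does not cure. Nor do the documents support calling these claims the trial's main reassurance on harm. What the defence does not supply is any PP check on the two rules, or a reason for omitting it that applies to non-inferiority.

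**Conclusion.** The gap is real. The superiority rationale for confining PP to the primary endpoint does not extend to the non-inferiority claims in 9.3.1.8 and 9.3.2.3, and nothing else in the SAP or Addendum fills it. In the base case, false claims under the SAP's rule rise by about 3 percentage points with 10% violators and about 8 points with 20%. That rests on an assumed violator share, no contrast in any of them, and the full 1800 patients. With half the contrast retained the rise is about 1.4 and 3 points, and with a larger excess in violators it reverses. The finding is a missing robustness check on a formal claim. It does not show that the claim is invalid, or that PP should replace the FAS.

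**What to change.** In 9.1, 9.3.1.8 and 9.3.2.3, pre-specify a repeat of the non-inferiority analyses on the PP set: RRT incidence, and mortality at Days 30, 90 and 180. For these repeats exclude violators entirely, because the rule in 6.3 of using data up to the violation has no clear meaning for mortality to Day 180. Report the PP result beside the FAS result, and state that non-inferiority will not be claimed without qualification if the two sets disagree. Keep the superiority tests on the FAS. Whether agreement of both sets should be a strict condition is debatable, given the loss of randomisation in PP; a supportive analysis that qualifies the claim is enough.

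The cost is at least four reruns of existing models, more if the selected-arm and Part 2 repeats are included. The PP test itself has about 3 points less power at true equality with 10% excluded, so an unqualified claim is slightly harder to reach. The PP comparison is also open to selection bias and has to be read as support for the FAS.

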9.2 Primary Endpoint

• Vasopressor- and mechanical ventilator-free days (P&VFDs) up to day 30

This composite endpoint is defined as the number of days (reported to one decimal place (0.0 to 30.0)) from start of treatment with the investigational medicinal product (IMP) [selepressin or placebo] to 30.0 days thereafter during which the patient is: 1) alive; 2) free of treatment with intravenous vasopressors; and 3) free of any invasive mechanical ventilation (see definition below).

Patient Death

By definition, any patient that dies within this 30-day period will be assigned zero P&VFDs, even if there is a period during which the patient is alive and free of both vasopressor treatment and mechanical ventilation.

Definition of "Free of Vasopressors"

Free of vasopressors means less than 60 minutes during any contiguous 24-hour period (regardless of calendar day). If a patient requires periods of vasopressors longer than 60 minutes in total during any 24-hour period, the intervening intervals during which they are free of vasopressors will not be included in the period free of vasopressors in the determination of the number of P&VFDs. Thus, the period free of vasopressors begins at the end of the last use of vasopressors that was either: 1) longer than 60 minutes in duration; or 2) part of greater than 60 minutes of use within a contiguous 24-hour period.

Norepinephrine/noradrenaline, phenylephrine, dopamine, epinephrine/adrenaline, vasopressin, terlipressin, and IMP (i.e. selepressin and placebo) all constitute a vasopressor for the purpose of the primary analysis.

Vasopressor use due to anaesthesia or procedure-induced hypotension during and up to three hours after a surgery or procedure (including bedside) is exempt from this rule (i.e. such use of vasopressors would not affect the calculation of P&VFDs).

Date: 20 Nov 2017 E-Statistical Analysis Plan-17877; Ver.9.0 Supersedes: Ver. 8.0

Page 24 of 80

Definition of "Free of Mechanical Ventilation"

Mechanical ventilation is defined as use of endotracheal or tracheostomy tube assisted ventilation (>5 cm H₂O continuous positive airway pressure and >5 cm H₂O of pressure support from the ventilator in tracheostomy patients). End of mechanical ventilation is defined as: 1) extubation of intubated patients or 2) \leq 5 cm H₂O continuous positive airway pressure and \leq 5 cm H₂O of pressure support from the ventilator in tracheostomy patients. If non-invasive ventilation by mask or bag (>5 cm H₂O of pressure support) is deployed to avoid (re)intubation, it also counts as mechanical ventilation. However, all other uses of non-invasive ventilation such as chronic night-time use of positive airway pressure for chronic obstructive pulmonary disease (COPD) or sleep apnea does not count as mechanical ventilation (regardless of pressure). Free of mechanical ventilation means less than 60 minutes during any contiguous 24-hour period (regardless of calendar day). If a patient requires mechanical ventilation for periods longer than 60 minutes in total during any 24-hour period, the intervening intervals during which they are not receiving mechanical ventilation will not be included in the period free of mechanical ventilation in the determination of the number of P&VFDs. Thus, the period free of mechanical ventilation begins at the end of the last use of mechanical ventilation that was either: 1) longer than 60 minutes in duration; or 2) part of greater than 60 minutes of use within a contiguous 24-hour period.

The use of mechanical ventilation associated with anaesthesia or procedural sedation during and up to three hours after a surgery or procedure (including bedside) is exempt from this rule (i.e. such use of mechanical ventilation would not affect the calculation of P&VFDs).

It is important to note that the determination of freedom from vasopressors and freedom from mechanical ventilation are made separately; in other words, periods of vasopressor use and mechanical ventilation are not combined when determining whether 60 minutes of use has occurred within a 24-hour period.

Missing data during the time of hospitalization will be imputed using a worst case approach taking into account previous and subsequent starting and stopping times of vasopressor administration and mechanical ventilation (see Figure 2). If only the stop date but not time is given, the imputed time will be midnight of that date (example A), unless a subsequent starting time was recorded prior to midnight in which case the imputed time would be the start time of the subsequent record (example B). If neither stop date nor time is given, the imputed stop time will be the start date and time of the subsequent recording. Likewise, missing start dates and times would be imputed as worst case scenarios, i.e. is the patient found to be on mechanical ventilation with a date but no time for intubation, the imputed start time would be recorded as 00:01 of that day or the stop date of a preceding recording on that same date, whichever occurs last. If both start date and time is missing, the imputed start time would be the date and time of the preceding stop time recorded. In case of data being completely missing from a certain time point and onwards, the "last status carried forward" imputation (example C) will be applied. If a patient was last seen on either ventilator or vasopressors, it is assumed that the patient remained so, and is imputed to a value of 0 (zero) P&VFDs. If the patient was last seen off ventilator and vasopressors, it is also assumed that the patient remained so in the remaining 30-day period. If the patient was last seen (alive) on e.g. day

Page 25 of 80

10 and at that point had been off both ventilator and vasopressors for three days, a value of 23 P&VFDs is imputed.

[figure not shown]

Figure 2: Missing Data Imputation of P&VFDs (Examples)

9.2.1 Primary Variable Analysis

The primary endpoint, P&VFDs, will be analyzed using a van Elteren test, stratified by need for ventilation (Yes/No), time from onset of shock (onset of any vasopressor) to start of treatment (< or \ge 6 hours), and norepinephrine/noradrenaline requirement at baseline (< or \ge 30 μ g/min).

The primary analysis will compare all patients on all selepressin arms from both parts of the trial (pooled together and treated as a single arm) to all patients on the placebo arm from both parts of the trial (see Appendix 7 for a discussion on treatment estimate bias).

The primary analysis will be a test of superiority using a two-sided 5% significance level test.

Treatment effects will be estimated assuming a negative binomial distribution (to allow for possible overdispersion in a Poisson distribution) for the quantity (30 minus P&VFDs) for survivors, and a binomial distribution to model the probability of surviving. Both models adjusted for need for ventilation (Yes/No), time from onset of shock to start of treatment (< or \geq 6 hours), and norepinephrine/noradrenaline requirement at baseline (< or \geq 30 µg/min) (see Appendix 3 for details). For completeness, the proportion of patients dying, and the P&VFDs for survivors will also be presented.

Page 26 of 80

Furthermore, P&VFDs will be tabulated by treatment arm (including pooled active treatment arms), and presented graphically by histograms and cumulative distributions functions.

The success (statistical/clinical significance) of the trial will be based upon the comparison of the analysis above (all patients on all selepressin arms from both parts of the trial (pooled together and treated as a single arm) compared to all patients on the placebo arm from both parts of the trial).

